[name] [name] FMedSci, Institute of Inflammation and Ageing, Professor of Immune Cell Biology, Director of the MRC-Versus Arthritis Centre for Musculoskeletal Ageing Research

[name] BSc MBBS MRCP(Geriatrics) PhD, Institute of Inflammation and Ageing, Clinician Scientist and Visiting Consultant in Geriatric Medicine (acting as Clinical Lead)

Title

An uncontrolled open label trial of a nutritional supplement to reduce biological and immune ageing in healthy older people

Background

Ageing of the immune system has long been held as a key mechanism in organisms as they age (Lopez-Otin et al. 2013). Age associated dysregulation of the immune system contributes towards an increased susceptibility of older adults to infectious diseases, reduced ability to respond to vaccinations and increased risk of autoimmune inflammatory diseases such as Rheumatoid Arthritis (Franceschi and Campisi 2014). Immune ageing also results in an increase in another key hallmark of ageing, cellular senescence, resulting in senescent cells accumulating across different organs (Yousefzadeh et al. 2021). Both immune ageing and cellular senescence contribute to an increase in circulating levels of pro-inflammatory cytokines, and reduction in the circulating levels of anti-inflammatory cytokines, termed "Inflammaging" (Franceschi and Campisi 2014). The degree of inflammaging is associated with increased risk or a wide range of age-related diseases as well as physical frailty (Wilson et al, 2017).

Therefore, immune ageing is a correlate of global biological ageing and indeed may be a key driver of age-related morbidity. Studies in mice in which senescence was induced only in T cells resulted in mice developing and aged phenotype and multimorbidity (Desdin-Mico et al. 2019). Immune ageing can now be reliably quantified using a combination of biological parameters to describe the so-called inflammatory immune age (i-AGE) of a person and compared to that person's chronological age (Sayed et al. 2021). Global biological ageing can also be measured through specific epigenetic markers, namely DNA methylation at specific sites, termed an epigenetic clock (Horvath 2013).

This trial will test the hypothesis that a combination of vitamins and nutraceuticals ("Essentials"), all known to have an effect on immune ageing or systemic inflammation will improve both biological markers of immune and biological age, and markers of physical function and general well-being (Studenski et al. 2011).

Research question

Does a 12-week course of a nutraceutical product containing a combination of vitamin D3, vitamin B3 (niacinamide), vitamin C, omega 3 fatty acids (DHA/EPA), olive polyphenols, resveratrol and astaxanthin improve measures of biological and immune ageing, quality of life, and physical function (Short Physical Performance Battery, SPPB) in healthy older people?

Objectives

To test the hypothesis that a 12-week treatment of Essentials, a nutritional supplement developed by Bayer, will improve biological ageing, immune ageing, quality of life (QoL), and physical function (SPPB) in healthy older adults, by conducting an uncontrolled open label trial in 76 participants.

Essentials composition:

- Vitamin D (20 μg)
- Vitamin C (85 mg)
- Vitamin B3, as niacinamide (50 mg)
- Omega 3 PUFA, EPA + DHA (250 mg)
- Resveratrol (30 mg)
- Olive fruit extract (50 mg), delivering hydroxytyrosol (10 mg)
- Astaxanthin (3.2 mg)

Outcome

An uncontrolled open-label trial, of a 12-week intervention of the Essentials supplement.

85 participants will be recruited to allow for 9 drop outs.

Data will be collected pre-intervention to test:

- Biological ageing by DNA methylation in peripheral blood and saliva;
- Immune ageing by measuring 51 different serum cytokines, chemokines and growth factors to give an iAGE score (Sayed et al 2021), hs-CRP will also be measured;
- QoL (SF36) and diet (7 day food diary, to confirm there was no significant change in the diet of the participants) from questionnaires;
- Physical function assessed by the SPPB (Guralink et al. 1994).

Data collection will be repeated after the 12-week intervention, with the exception of QoL questionnaires which will additionally also be taken at 4 and 8 weeks in to the intervention.

Data analysis will compare differences within groups between pre-intervention and 12 week measures.

Venous blood will be collected to process serum and will also be collected in to a PAX tube for isolation of DNA. The serum will be used for measurement of the inflammatory immune clock of ageing (iAGE) which is based upon the levels of 51 different cytokines, chemokines and growth factors (Sayed et al. 2021). The measurement will be carried out using a multiplex based methodology. The DNA isolated from the PAX tube will be analysed for DNA methylation using the Illumina EPIC array and the data analysed using both the Horvath (Horvath 2013) and Hannum (Hannum et al. 2013) epigenetic clocks of biological ageing. A second assessment of epigenetic age will be conducted on saliva samples by the company Chronomics. The difference between

chronological age and iAGE will then be calculated as a measure of immune ageing and the epigenetic clock age will establish the degree of overall biological ageing. High sensitivity C-reactive protein from blood will be measured by ELISA.

Study setting

Participants will be invited to attend the Clinical Research Facility at the University Hospital Birmingham where all trial procedures will take place.

Participant recruitment

Eligibility Criteria

The study population is healthy older people.

Inclusion criteria

- Age ≥60 years.
- Ability to provide informed consent.
- Willing to stop taking multivitamins, and dietary supplements containing vitamins C and D, B3, DHA/EPA, Olive polyphenols, resveratrol and astaxanthin or food/beverage products supplemented with the above ingredients 2 weeks prior to and throughout the study.
- Able to travel to the clinic for initial and subsequent evaluations.

Exclusion criteria

- Current smokers, or ex smokers who have stopped within the last 12 months, or are using nicotine replacement products.
- History of diabetes, myocardial infarction, congestive heart failure, kidney failure, liver disease or stroke.
- Untreated thyroid disorder, cancer, active neoplasms.
- Untreated gastrointestinal, or pulmonary diseases.
- Surgery or trauma in last 60 days.
- Inflammatory diseases, auto immune diseases or recent infection in last 60 days.
- Allergies to any of the ingredients to be studied.
- Currently taking or using multivitamins or dietary supplements containing vitamins C and D, B3, DHA/EPA, Olive polyphenols, resveratrol and astaxanthin or food/beverage products supplemented with the above ingredients.
- Currently taking medication known to be metabolised by CYP3A.
- Currently taking any of the following medications, which confound the effects of inflammation: Tamoxifen, Cyclosporine A, immunosuppressants or Anti TNF inhibitors, NSAIDs.
- Currently taking any of the following anticoagulant drugs (blood thinners): Warfarin, Direct oral anticoagulant drugs (DOACs), and antiplatelet drugs including aspirin.
- Individuals at risk of bleeding complications, including those with inherited bleeding disorders (such as haemophilia), or increased risk hemorrhagic stroke or events.
- Unable or unwilling to maintain current lifestyle throughout study such as eating habits, exercise habits, etc.
- Assessed as being frail by Fried phenotype criteria.

Recruitment target

76 healthy older adults required, so we will aim for 85 recruited to allow for drop outs.

Size of recruitment target

Our sample size calculation is based on iAGE measurements from a previous study of a nutraceutical intervention in adults by Bayer. The number of participants required at 80% power and a significance level of 0.05 to detect a mean difference of 1.5 years in the iAGE score would be 76. To allow for an approximate 10% drop out we will recruit 85 participants.

Recruitment technique

Participants will be invited by contact through the 1000 Elders database. The 1000 Elders is a database of research active healthy older people who have consented to be contacted about studies run through the University of Birmingham. Names, addresses and contact details (telephone and email) are stored complying fully with DPA and CPRD legislation. The invitation will be in the form of an email. This will include an attached PIS, summary of the study, and an invitation to contact the research team if they would be interested in taking part.

Recruitment

Potential participants will contact the study team via email or telephone to express an interest to join the study. At this point eligibility screening will take place, either by telephone or through email communication

Participant identification

Eligible people will then be invited to the Clinical Research Facility at Queen Elizabeth Hospital Birmingham for the initial visit. Reasonable travel expenses will be paid to participants.

Consent

At the initial visit eligibility will be confirmed and informed consent will be gained for all activities in the trial. The nature and objectives of the study will be explained, and potential risks discussed. This information will be presented in a written patient information sheet (PIS) sent to potential participants prior to the in person visit, giving participants time to consider their participation. The process for withdrawal, including the subsequent impact on data and sample storage will be described.

At this point capacity to consent to be in the trial will be assessed. Participants will then sign a written consent form, and a copy of the information sheet and consent form given to them, and other copies stored in the trial file.

	Assessment periods	
Visits	1 (Baseline, in person)	V2 (Week 12, in person)
Time per session	Max 2 hr	Max 1 hr
Day	0	84
Medical history, incl. Concomitant medication	Х	
Assessment of inclusion/exclusion criteria	Х	
Informed consent	X	
SPPB	х	х

Qol questionnaire (also to be filled in at wk 4, 8)	х	х
7 day food intake questionnaire*	X	x
Blood	X	x
Saliva	X	X
Vital signs/bmi	Х	х
Adverse event reporting		Х
Capsule distribution	X	
Compliancy pill count		х

^{*}Food diary to be returned at V2

Data Protection and Confidentiality

All laboratory specimens and case record forms will be identified in a manner designed to maintain participant confidentiality. Laboratory specimens will arrive at the lab in a pseudo anonymised form. The anonymisation will be done by the person taking the sample. All records will be kept in a secure storage area in the Institute of Inflammation and Ageing with limited access to study staff only. Information will not be released without the written permission of the participant, except as necessary for monitoring and auditing by the Sponsor, its designee or Regulatory Authorities. The CI and study staff involved with this study will not disclose or use for any purpose other than performance of the study, any data, record, or other unpublished, confidential information disclosed to those individuals for the purpose of the study.

The CI and study staff involved with this study will comply with the requirements of the Data Protection Act 2018 with regard to the collection, storage, processing and disclosure of personal information and will uphold the Act's core principles. Access to collated participant data will be restricted to the CI and appropriate study staff.

Computers used to collate the data will have limited access measures via user names and passwords.

Published results will not contain any personal data that could allow identification of individual participants.

GP Notification

We will inform he GP of the participants involvement in the study if the participant consents to this

Safety reporting

An adverse event (AE) is any untoward medical event affecting a clinical trial participant. Each initial AE will be considered for severity, causality or expectedness and may be reclassified as a serious event or reaction based on prevailing circumstances.

An adverse reaction (AR) is where it is suspected that an AE has been caused by a reaction to the trial supplement

A serious adverse event (SAE), serious adverse reaction (SAR) or suspected unexpected serious adverse reaction (SUSAR) is any AE, AR or UAR that at any dose:

- results in death
- is life threatening
- requires hospitalisation or prolongation of existing hospitalisation
- results in persistent or significant disability or incapacity
- is a congenital anomaly or birth defect
- Or is otherwise considered serious

Note: Hospitalisations for treatment planned prior to consent and hospitalisation for elective treatment of a pre-existing condition will not be considered as an SAE. However any adverse events occurring during such hospitalisation will be recorded. Adverse events, adverse reactions and serious adverse events will be reported by participants or other health care professionals.

A telephone contact will be made at 4 and 8 weeks to ensure no adverse events are missed.

All AEs and SAEs will be recorded from the time a participant consents to join the study until the last study visit. Participants with unresolved AEs at the last study visit will be followed up until resolution or 30 days after last visit of that participant, whichever is sooner. SUSARS will be followed until resolution.

The CI, or delegate will ask about the occurrence of AEs and hospitalisations at every telephone check (week 4 and 8) and at the second/final study visit (week 12). AEs will be recorded on the AE Log in the CRF. SAEs will be submitted on an SAE form to the Sponsor within 24 hours of becoming aware of the SAE. SAEs will be assessed for expectedness and causality by the Investigator. The evaluation of expectedness will be made based on the knowledge of the reaction and the relevant product information.

The Sponsor, together with the CI, is responsible for reporting SUSARs to the competent authority, the Research Ethics Committee (REC) and any other competent authorities. Fatal or life threatening SUSARs will be reported within 7 days and non-fatal and non-life threatening SUSARs within 15 days.

Ethical and regulatory considerations

The trial will fit within existing ethical and regulatory frameworks. Participants are healthy volunteers, and not recruited as NHS patients. However, as the recruitment and assessments will take place within an NHS institution we will secure approval through the Health Research Authority (HRA) and an NHS Research Ethics Committee (REC).

The trial product is a nutraceutical, and all components are safe. As such we do not expect the product to present any risks to participants. There are potential benefits to the participants from the product. Application will be made for ethical approval through the HRA, NHS REC, and Hospital trust approval through R+D and Clinical Research Facility governance processes. The study will be sponsored by the University of Birmingham.

Assessment and management of risk

Resveratrol	Minor or none, GI adverse effects in high doses. Safe up to 450mg/day, does in trial is 30mg/day. Resveratrol has been shown to inhibit metabolism of drugs through the CY3PA enzyme. There is a risk of interaction with drugs metabolised by CYP3A if doses >1000mg/day, and long term.
	Studies up to 12 months
Astaxanthin	Minor or none serious adverse effects reported (GI – increased bowel movements, red stool colouration). Safe up to 8mg/day, dose in trial 4mg/day No recognised drug interactions.
	Studies up to 24 months
Vitamin C, D and B3	No concerns about safety at trial doses
Olive derived polyphenols	No concerns about safety
DHA and EPA	Theoretic risk if >6g/day of interaction with warfarin, but no evidence found in reviews. Dose in trial 250mg/day

Full safety details in Appendix 1

To mitigate any potential risks of drug interactions we will exclude people taking anticoagulants, antiplatelets, or drugs metabolised by the CYP3A system

Research Ethics Committee (REC) and other Regulatory review & reports

Before the start of the study, a favourable opinion will be sought from UK NHS Health Research Authority and NHS REC for the study protocol, informed consent forms, patient information sheets, and initial invitation.

Substantial amendments that require review by NHS HRA and REC will not be implemented until that review is in place and other mechanisms are in place to implement at site. All correspondence with the HRA will be retained. It will be the Chief Investigator's (TJ) responsibility to produce the annual reports as required. The Chief Investigator (TJ) will notify the HRA of the end of the study. If the study is ended prematurely, the Chief Investigator (TJ) will notify the HRA, including the reasons for the premature termination. Within one year after the end of the study, the Chief Investigator (TJ) will submit a final report with the results, including any publications/abstracts, to the HRA.

Regulatory Review & Compliance

Before we enrol participants into the study, the Chief Investigator (TJ) will ensure that appropriate approvals from participating organisations are in place. Specific arrangements on how to gain approval from participating organisations are in place and comply with the relevant guidance. Different arrangements for NHS and non NHS sites are described as relevant.

Amendments

Any amendments will be the responsibility of the Chief Investigator (TJ). The CI will seek Sponsor approval for any amendments to the Protocol or other study documents. The Sponsor will decide if the amendment is substantial, or non-substantial. These will then be notified to the HRA in line with current guidance. http://www.hra.nhs.uk/resources/after-you-apply/amendments/

Amendments to the protocol or other study docs will not be implemented without approval from the Sponsor and subsequent approval from the appropriate REC and/or Regulatory Authority, as appropriate, and NHS R&D Office.

Conflict of interests

[name] as key investigator/collaborator of this study declares her role as a Consultant for Bayer Pharmaceuticals. She reports receiving consultancy fees from Bayer Pharmaceuticals during the preparation and upcoming conduct of the proposed study. [name] will not be involved in Adverse Event assessment in deciding causality. The Chief Investigator [name] will be assessing causality. Bayer Pharmaceuticals shall provide the nutritional supplement but will have no role in conduct, analysis and write-up of the results. As per Good Clinical Practice conflicts of interest will be reported at all levels of dissemination (including publications and University of Birmingham communications) relating to this study.

Funding arrangements

This study is funded by a research grant from Bayer Healthcare Pharmaceuticals

Peer review

This protocol has undergone both internal (within the Institute of Inflammation and Ageing) and external peer review

Protocol Deviations and Breaches

The CI will not implement any deviation from the protocol without agreement from the Sponsor, except where necessary to eliminate an immediate risk to trial participants.

In the event that the CI needs to deviate from the protocol, the nature of and reasons for the deviation will be recorded in the CRF, documented and notified to the Sponsor. If this necessitates a subsequent protocol amendment, this will be submitted to the Sponsor for approval and then to the appropriate REC, Regulatory Authority and local NHS R&D for review and approvals as appropriate.

In the event that a serious breach of the protocol or GCP is suspected, this will be reported to the Sponsor immediately.

End of Study and Archiving

The end of study is defined as last patient last visit. The Sponsor and CI have the right at any time to terminate the study for clinical or administrative reasons.

The end of the study will be reported to the Sponsor, REC, Regulatory Authority and NHS R&D Office(s) within 90 days, or 15 days if the study is terminated prematurely.

Archiving of study documents will be carried out as specified in UoB-ARC-SOP-001 Standard operating Procedure: Archiving . All study documentation will be kept for 110years.

Access to the final data set

The final data set will be available on request to the CI

Dissemination plans

The clinical study report will be used for publication and presentation at scientific meetings.

Summaries of results will also be made available to Investigators for dissemination within their clinical areas (where appropriate and according to their discretion).

Authorship Eligibility Guidelines

Ownership of the data arising from this study resides with the study team and their respective employers. On completion of the study, the study data will be analysed and tabulated, and a clinical study report will be prepared.

Authorship eligibility for each manuscript arising from this study will be determined according to the criteria laid out in the Working Practice Document on Authorship filed in the Study Operations Manual.

We have no plans to use professional writers

References

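### The food diary is meant to confirm that diet did not significantly change, but a non-significant comparison in 76 people cannot confirm stability; report the estimated change with its confidence interval instead

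*Protocol*

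**What the plan says.** The Outcome section lists the diet measure among the data collected before the intervention and again after 12 weeks, and states its purpose in a parenthesis: "7 day food diary, to confirm there was no significant change in the diet of the participants". The one sentence on analysis in that section is general to all measures: "Data analysis will compare differences within groups between pre-intervention and 12 week measures". The same section describes the design: "An uncontrolled open-label trial, of a 12-week intervention of the Essentials supplement".

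The only significance level in the protocol is under Size of recruitment target, where it belongs to the iAGE calculation: "80% power and a significance level of 0.05 to detect a mean difference of 1.5 years in the iAGE score would be 76". The protocol gives no dietary variable, test, margin or confidence-interval rule for the diary.

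Two other provisions bear on diet. The inclusion and exclusion criteria keep out current users of supplements, or of foods and drinks fortified with the product's ingredients. Participants must be willing to go without them from two weeks before the study until it ends. The exclusion criteria also remove anyone "Unable or unwilling to maintain current lifestyle throughout study such as eating habits, exercise habits, etc".

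**The concern.** Confirming that something did not change is an equivalence aim. A test of no difference answers another question: whether the data are strong enough to reject zero change. Failing to reject may mean that diet was stable, or only that the diaries were noisy or few. A rule that treats non-significance as confirmation is easier to satisfy with poorer data.

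This matters here because there is no control group. Several product components (vitamins C and D, niacinamide, EPA and DHA, olive polyphenols) can also come from ordinary food. The diary is the only measurement in the protocol that could show whether intake from food moved over the 12 weeks. If a moderate shift is declared absent, whatever it contributed to the change in iAGE, hs-CRP, SF36 or SPPB is credited to the supplement.

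**Working it through.** **Inputs.** From the protocol: n = 76 (85 recruited), significance level 0.05, one group measured at baseline and week 12. Assumed: the test is two-sided (the protocol does not say), it is a paired t-test, and all 76 completers supply two usable diaries. The protocol gives no SD for any nutrient, so shifts and margins are in SDs of the within-person change.

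**The plan's own figures.** 76 / 0.90 = 84.4, rounded up to 85, which agrees with the recruitment target. The 76 cannot be checked because no SD for iAGE is given. Working backwards, (1.960 + 0.842) / √76 = 0.321, so a 1.5-year difference implies an SD of change of 1.5 / 0.321 = 4.67 years. The trial is therefore sized to detect about 0.32 SD on iAGE. Nothing is sized for diet.

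**Chance that a real diet shift is non-significant.** For a true shift of d SDs, the t statistic is noncentral t with 75 degrees of freedom and noncentrality d√76. The result is non-significant when |t| < 1.992.

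| True shift d | d√76 | Non-significant, n = 76 | Non-significant, n = 50 |
|---|---|---|---|
| 0.20 SD | 1.74 | 59% | 72% |
| 0.25 SD | 2.18 | 42% | 59% |
| 0.30 SD | 2.62 | 27% | 45% |
| 0.50 SD | 4.36 | 1% | 7% |

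The n = 50 column is an illustration of incomplete diary return. It shows the chance of apparent confirmation rising as data are lost.

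**What a non-significant result leaves open.** The 95% CI half-width is 1.992 / √76 = 0.229 SD. An observed change just short of significance lies 0.229 SD from zero, so its far limit is 2 × 0.229 = 0.46 SD.

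**Whether an equivalence rule is workable.** The rule is that the 90% CI (half-width 1.665 / √76 = 0.191 SD) lies wholly inside a margin of ± m. Simulated pass rates with n = 76 and truly unchanged diet:

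| Margin m | Stability shown |
|---|---|
| 0.20 SD | 8% |
| 0.30 SD | 66% |
| 0.35 SD | 83% |
| 0.40 SD | 93% |

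**In product units, for illustration.** Take a margin of 25% of the daily EPA + DHA amount: 0.25 × 250 = 62.5 mg. If the SD of change were 300, 400 or 600 mg/day, the margin would be 0.21, 0.16 or 0.10 SD. Stability would then be shown 13%, 0.04% or 0% of the time even if diet had not changed. For vitamin C, 0.25 × 85 = 21.25 mg; with SDs of 40, 60 or 80 mg/day the margin is 0.53, 0.35 or 0.27 SD, and the pass rates are 99.7%, 84% or about 49%. The 25% and all the SDs are assumptions, and the spread shows how far the answer depends on them.

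**The case against.** The strongest reply is that the protocol never writes down the rule being criticised. It names no test, p-value or nutrient for the diary, and the word significant may simply mean material. The 0.05 level belongs to iAGE. Margins, interval rules and choice of nutrients are ordinary content for a statistical analysis plan, which is not shown.

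Much of this stands. A reader might infer that the protocol prescribes a test of no difference for diet; it does not, and that reading rests on the wording of the purpose taken with the general sentence on analysis. The absence of a margin is not in itself a finding. What remains is the stated purpose. A plan that followed it literally would report a failure to reject as confirmed stability. If significant means material, the sentence still gives nothing by which material could be judged.

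It is also fair to say that the protocol does more about diet than keep a diary. The bar on supplements and fortified products and the lifestyle exclusion address the same nutrients. They make a shift less likely, but they set conditions on willingness and intended behaviour and do not verify what people ate.

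Finally, diet is a supporting check and not one of the objectives. Even proven stability would leave time, season, regression to the mean and expectation as explanations in a trial without a control. That limits the weight of the point without removing it.

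**Conclusion.** The point holds as a fault in the stated inferential aim. With 76 paired diaries, non-significance cannot confirm stable diet: true shifts of 0.20 to 0.30 SD would go undetected 59% to 27% of the time, and shifts up to about 0.46 SD remain compatible with a just non-significant result. These figures assume a two-sided paired t-test at 0.05 and complete diary pairs.

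The tempting stronger conclusion is that diet would be wrongly cleared. The documents support only that it could be. A shift of 0.50 SD would be missed 1% of the time, and nothing in the protocol says that a non-significant result will be taken to rule diet out. Nor do the documents show that diet is likely to shift, or by how much; the illustrations in nutrient units rest on assumed SDs. This is worth correcting because it changes what the trial may conclude, but it is not a threat to the main analysis.

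The calculation also presumes that a baseline diary exists. The assessment table lists the diary at both visits, with the footnote "Food diary to be returned at V2". That timing question is separate and should be clarified on its own account; the point here would hold with a correctly timed diary.

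**What to change.** Reword the diary's purpose in the Outcome section so that it is there to estimate the change in diet over the 12 weeks. For the diary nutrients that are also in the product, report the mean change with its confidence interval and the number of paired diaries. State that a non-significant p-value will not be reported as evidence of stable diet. This uses data already planned and costs no participants or visits.

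If the sponsor wants to claim stability, it should fix a margin for each nutrient before the data are analysed and make the claim only if the whole 90% CI lies inside it. The margin should be checked against a plausible SD of change first. At n = 76 a margin of about 0.35 SD or wider is needed for a better than 80% chance of success when diet is truly unchanged, so a margin tied to a small fraction of the product's daily amount may be unattainable for some nutrients.

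Regressing each outcome's change on the participant's own diet change is optional. It is supportive only, because error in the diaries makes the adjustment partial.

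The downside is that the report may have to say that dietary stability was not shown.

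### Two exclusion lines bar disease only while it is untreated and set no period of stable treatment, so a response to newly started treatment can enter the single-arm change from baseline

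*Protocol*

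**What the plan says.** The protocol's Exclusion criteria contain four lines that name diseases.

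- Two depend on treatment status: "Untreated thyroid disorder, cancer, active neoplasms" and "Untreated gastrointestinal, or pulmonary diseases". Neither gives a minimum time on treatment or a period of unchanged treatment.
- Two do not depend on treatment: "History of diabetes, myocardial infarction, congestive heart failure, kidney failure, liver disease or stroke" and "Inflammatory diseases, auto immune diseases or recent infection in last 60 days".

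The same list sets look-back windows for other things. It uses 12 months for smoking and 60 days for recent infection and for surgery or trauma ("Surgery or trauma in last 60 days"). It also bars certain drugs, including "Currently taking medication known to be metabolised by CYP3A" and "Tamoxifen, Cyclosporine A, immunosuppressants or Anti TNF inhibitors, NSAIDs". The lifestyle criterion gives eating and exercise as its examples and does not mention medication.

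The Outcome section fixes the comparison: "Data analysis will compare differences within groups between pre-intervention and 12 week measures". There is one arm and it is open label. The visit schedule records medical history and concomitant medication at Visit 1.

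**The concern.** A disease that stops being an exclusion once treatment begins lets in people whose baseline is taken while they are still responding to that treatment. Someone who started thyroid, gastrointestinal or pulmonary treatment the week before Day 0 is no longer untreated. Unless a drug exclusion happens to catch the medicine, that person qualifies.

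In a randomised trial such people would fall into both arms and largely cancel. Here their change between Day 0 and Day 84 goes straight into the estimate attributed to the supplement, and no later analysis of the group as a whole can take it out. The plan already guards against recent change in smoking, surgery, trauma, infection, diet and exercise. Recently started treatment is the same kind of disturbance and is not covered.

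**Working it through.** **1. Reading the criteria.** I checked each exclusion for a rule on treatment duration or stability.

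| Criterion | Depends on treatment? | Stops a recent starter? |
|---|---|---|
| Thyroid, cancer, neoplasms line | Yes, at least for thyroid | No |
| Gastrointestinal or pulmonary line | Yes | No |
| Diabetes, cardiac, kidney, liver, stroke line | No, barred by history | Not needed |
| Inflammatory, autoimmune, infection line | No | Not needed |
| Drug exclusions | By drug class | Only if the drug is on the list |
| Surgery or trauma, 60 days | By event date | Only if treatment was surgical |
| Lifestyle rule | Eating, exercise | No mention of medication |

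No criterion sets a stability period for treatment.

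**2. The plan's own figure.** The section on the size of the recruitment target gives 76 participants for a 1.5-year mean iAGE difference at 80% power and a significance level of 0.05. No SD is stated, so 76 cannot be reproduced forward. Solving backwards for a paired comparison:

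SD = 1.5 × √76 / (1.960 + 0.842) = 1.5 × 8.718 / 2.802 = 4.67 years (normal, two-sided).

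The t-test version gives 4.61 years, which I use below. (A one-sided normal test would imply 5.26.) The recruitment figure does reproduce: 76 / 0.90 = 84.4, rounded up to 85.

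**3. Size of the bias.** If k of 76 participants are recent starters and each changes by s years because of that treatment, the spurious mean change is k × s / 76. The protocol gives neither k nor s, so both are assumed. The last column is the chance of a significant improvement when the supplement does nothing. It comes from simulating 76 normal changes with SD 4.61, k of them shifted by s, and a two-sided t-test at 0.05 (400,000 simulated trials per row). With no recent starters it is 2.5%.

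| k | s (years' fall) | Spurious mean fall | Share of 1.5 years | False improvement |
|---|---|---|---|---|
| 1 | 1.5 | 1 × 1.5 / 76 = 0.02 | 1% | 2.7% |
| 2 | 3 | 2 × 3 / 76 = 0.08 | 5% | 3.4% |
| 2 | 5 | 2 × 5 / 76 = 0.13 | 9% | 4.1% |
| 2 | 10 | 2 × 10 / 76 = 0.26 | 18% | 5.7% |
| 4 | 5 | 4 × 5 / 76 = 0.26 | 18% | 6.4% |
| 4 | 10 | 4 × 10 / 76 = 0.53 | 35% | 11.6% |

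If treatment moved iAGE the other way, the bias would reverse and the chance of a false improvement would drop below 2.5%.

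**4. SF-36, for illustration.** Assume an SD of change of 10 points and 4 recent starters gaining 15 to 25 points each; none of these figures is in the protocol. The mean rises by 4 × 15 / 76 = 0.8 to 4 × 25 / 76 = 1.3 points, and false improvement is about 8% to 13%.

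**The case against.** The strongest reply is that the affected group is small. The diseases most closely tied to an inflammatory score are barred whatever their treatment. CYP3A substrates, NSAIDs, immunosuppressants, anticoagulants and antiplatelets are barred, as are frailty and recent surgery, trauma or infection. Volunteers come from a database of healthy older people. Nothing in the protocol shows that any recent starter would enrol. A fall of 5 to 10 years per person is 3.3 to 6.7 times the 1.5-year target, and nothing in the protocol supports it. Inputs closer to that target (1 to 2 people, 1.5 to 3 years) barely move the error rate. All of this stands, and it is why the point is modest. It does not close the gap: those filters work by disease, drug class or event, not by when a treatment began, so permitted treatments still get through.

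Three stronger readings are tempting, and the documents do not support them.

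- *All the disease exclusions depend on treatment status.* Only two of the four do.
- *Someone who has just finished cancer treatment is admitted.* This depends on whether *untreated* governs the whole line or only thyroid disorder. On the second reading cancer is barred whatever its treatment. The line is ambiguous, which is itself a reason to reword it.
- *The bias certainly favours the product.* Improvement in quality of life or physical function after effective treatment is plausible, but nothing in the protocol says that thyroid, gastrointestinal or pulmonary treatment lowers a 51-marker score.

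It may also be said that the uncontrolled design is the root cause and is openly declared. That is true, but it makes avoidable background change more worth removing, and eligibility is fixed in the protocol.

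**Conclusion.** The point holds as a cheap improvement. Two exclusion lines admit people who have recently started permitted treatment, no stability period appears anywhere, and the single-arm comparison cannot separate their response from the supplement's effect. The size cannot be determined from the documents. For iAGE, under the assumed inputs above and the implied SD of 4.61 years, the spurious mean improvement is 0.02 to 0.53 year and the chance of a false improvement is about 3% to 12% instead of 2.5%. The upper end needs 4 recent starters who each fall by 10 years; with few starters or small responses the bias is negligible. The direction for iAGE and hs-CRP is unknown. For SF-36 and SPPB, improvement is the more plausible direction, but that too is a judgement, not something the protocol states.

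**What to change.** Reword the two lines so that they:

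1. say plainly whether *untreated* applies to cancer and active neoplasms or only to thyroid disorder;
2. exclude thyroid, gastrointestinal or pulmonary disease that is untreated, or whose treatment was started or changed within a stated look-back before Day 0.

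The investigators should choose the length of the look-back, consistent with the other windows in the list. It can be checked from start dates in the concomitant-medication record already taken at Visit 1.

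A requirement that every regular medicine be unchanged before entry would be broader than the problem shown. It would defer people for changes with no demonstrated link to the outcomes.

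The cost is an amendment to two lines, a start-date field if the record lacks one, and the deferral of a few volunteers. No visit, assay or extra participant is needed.
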